***First and last labs for HIV-infected patients receiving naltrexone and antiretroviral medications***

Labs	N	Median At First date (IQR)	Median At Last Date (IQR)	P- Value*
CD4	58	323 (156-573)	441 (243-612)	.06
VL	54	1916 (399.7- 35977)	879 (75- 16582)	.3
AST	52	53 (41-80)	66 (40-139)	.2
ALT	63	36 (21-74)	48 (33-115)	.2

In addition, in a recent 6-month randomized clinical trial (unpublished) evaluating buprenorphine/naloxone versus naltrexone therapy for the treatment of opioid dependence, 12 HIV-infected patients received naltrexone at a dose of 50 mg per day (**Schottenfeld RS, Chawarski MC, Mazlan M.** Maintenance treatment with buprenorphine and naltrexone for heroin dependence in Malaysia: a randomised, double-blind, placebo-controlled trial. *Lancet*. 2008;371(9631):2192-200). All were infected with Hepatitis C. No patients experienced adverse events that required changing the dose or discontinuing the medication. One patient experienced an isolated elevation in their ALT level.

Summary: Naltrexone treatment is associated with no significant adverse alterations in CD4, viral load, AST and ALT in HIV-infected patients who are receiving antiretroviral medication. The stability of these biological markers during naltrexone treatment supports safety when provided along with antiretroviral medications.

Interaction of NTX and alcohol: NTX has been shown to reduce the number of drinks consumed in the laboratory and in the clinic. No safety concerns have been identified in these studies when alcohol is consumed in combination with NTX. There is no evidence that individuals attempt to over-ride the effects of NTX by drinking more. NTX does not block the aversive effects of alcohol consumption which serve to limit drinking.

Counseling: There are no significant adverse effects of participating in the counseling intervention (MM/MC) portion of this study provided by the study nurse and supervised by a Clinical Psychologist. Participation is likely to be of benefit.

Breath screening, blood/urine collections: Breath screening and blood and urine collections are performed primarily as safeguards and should add no risks other than those normally associated with these procedures.

Rating scales and questionnaires: Rating scales, structured interviews, and questionnaires are all non-invasive, and should also add no risks to subjects, as our past experience indicates.

Audiotaped sessions: Participants will be made aware during the informed consent process that sessions with the study physician or nurse will be audiotaped and that the nature of these sessions will involve participants speaking about information regarding their health status, alcohol use, HIV status, medical history, and participation in the study. However, participant names will never be recorded on the tapes and the tapes will be coded by participant number rather than name in order to protect participant confidentiality. Participants will be given the option to decline to be taped during the study.

**2. Minimizing Risks:** Describe the manner in which the above-mentioned risks will be minimized.

Naltrexone (VIVITROL): Prospective participants with medical conditions that would contraindicate the use of VIVITROL will be screened out. We will exclude individuals with evidence of significant hepatocellular injury (AST, ALT > 5 times the upper limit of normal or a diagnosis of cirrhosis and Child-Pugh class greater than A or B). The dose of VIVITROL used is low and so the risk of hepatotoxicity is low. However, we will monitor liver enzyme tests prior to, during, and at end of treatment and a subject whose AST or ALT rises to > 5 times the upper limit of normal will have laboratory tests repeated in one week. If liver enzymes are persistently elevated or if the individual is symptomatic, study medication will be discontinued and the subject will be referred for GI evaluation.

As the safety of VIVITROL has not been established in pregnant and nursing women, they will be excluded from participation. Women of child-bearing capacity must agree to use a reliable form of birth control. A urine pregnancy test will be performed at baseline and monthly. Pregnant women will be referred for other alcohol treatment. Women who become pregnant during the study will be taken off study medications immediately. Individuals with urine tests positive for recent opioid use, who are taking opioid medication for the treatment of pain, or have a diagnosis of current opioid dependence will be excluded. In case of an emergency situation requiring opioids, subjects will be provided with a card showing that they are receiving VIVITROL. This card will provide detailed information to medical personnel describing the special precautions necessary in the event that the subject should require pain management. Specifically, the amount of opioids necessary for analgesia may be greater than usual, and the resulting respiratory depression may be deeper and more prolonged. As a result, a rapidly acting analgesic that minimizes respiratory depression is preferred and the amount of the analgesic administration titrated to the needs of the patient in a setting equipped and staffed for cardiopulmonary resuscitation. In addition, this card will have a code number on it that can be used to identify which medication the subject is on. A phone number of the pharmacy and for the physician on call for the study will be listed on the card in the event of an emergency in which it is necessary to determine whether the subject is on active VIVITROL.

Rating scales and questionnaires The major risk of the assessments is the potential loss of confidentiality which is discussed in the section related to confidentiality below. To minimize any discomfort associated with reporting on sensitive behaviors, participants will be informed that they may refuse to answer questions that they are not comfortable answering. Questions related to eligibility determination and monitoring of safety and treatment response are not optional. If a person declines to answer these questions, we will advise them that they will not be able to participate and we will make a referral to other treatment if they are interested.

APPROVED BY THE YALE UNIVERSITY IRB 10/11/2018 VALID THROUGH 10/13/2019  
Audiotaped sessions: All appropriate actions will be taken by staff members in order to minimize the risks associated with loss of confidentiality. Tapes will be coded by number and will be erased

Confidentiality: Numerous steps will be taken to protect confidentiality as described under the section on Sources of Materials (E.1.b). In addition, a Certificate of Confidentiality will be obtained from NIAAA. This certificate will protect the confidentiality of all research records generated by this study. Individually identifiable health information will be protected in accordance with the Health Insurance Portability and Accountability Act (HIPAA) of 1996. All research personnel will be trained on Institutional Review Board (IRB) and HIPAA procedures.

In Case of Injury: If a participant is injured as a direct result of participation in this study, treatment will be provided. The participant and/or his or her insurance carrier will be expected to pay the costs of this treatment. No additional financial compensation for injury or lost wages is available. Participants will not waive their legal rights by participating in this study.

All participants will be asked to carry a medication card that will, in case of emergency, alert the treating medical personnel that they are taking VIVITROL. Participants will be asked to carry this card at all times. The card will include appropriate drug information and precautions. If immediate information is needed about the study, participants will be instructed to contact either the study physician or nurse.

During the follow-up period, any patient requiring additional intervention due to significantly increased alcohol consumption or serious psychiatric/medical symptoms will receive a referral to treatment.

3. **Data and Safety Monitoring Plan:** Include an appropriate Data and Safety Monitoring Plan (DSMP) based on the investigator's risk assessment stated below. (Note: the HIC will make the final determination of the risk to subjects.) For more information, see the Instructions, page 24.

- a. What is the investigator's assessment of the overall risk level for subjects participating in this study? Moderate
- b. If children are involved, what is the investigator's assessment of the overall risk level for the children participating in this study? NA
- c. Data and Safety Monitoring Plan:

The risks associated with participating in this study can be categorized as moderate (i.e., risks are recognized as being greater than everyday risks but not high, and there is adequate surveillance and protections to discover adverse events promptly and keep their effects minimal). Because of the risks associated with this medication, we have included in the protocol procedures to exclude participants who would be at the greatest risk (e.g. concomitant significant medical conditions or liver dysfunction) and to monitor potential adverse effects and transfer patients to alternative treatment if medical problems possibly related to either of the study medications develop. The medical transfer procedure along with the procedures for detecting and responding to adverse events are sufficient to ensure prompt discovery of any adverse events and to minimize their effects. Consistent with the Data and Safety Monitoring Plan (DSMP) template of the Yale University School of Medicine, the DSMP includes provisions for data review and performance of safety reviews, as described below.

Data and safety monitoring procedures in this study include computerized data collection and monitoring systems and an organizational structure of clearly defined tasks assigned to all

APPROVED BY THE YALE UNIVERSITY IRB 10/11/2018 VALID THROUGH 10/13/2019  
research and clinical personnel involved in the conduct of this study. The computerized data collection and monitoring system consists of a data base system that records clinical and research activities, completion of scheduled assessments, and delivers computerized versions of most of research instruments used in this study. Research assistants use this database to monitor and schedule patients and activities and to administer study assessments. Data entry of non-computerized assessments is accomplished by using specialized data entry software (such as, SPSS Data Entry or Microsoft Access Data base) facilitating efficient data entry and allowing elimination of out-of-range values and double entry of data for detection of key punch errors.

The organizational structure used to ensure quality of data in this project include: 1) extensive training and close supervision of research assistants in data collection; 2) preliminary review of all data for completeness and coding errors by data manager/analyst; and 3) utilization of error-checking statistical procedures. Experienced data manager/analysts and the PI supervise data procedures. All error corrections are fully documented in the research records of the study. All research personnel are required to participate in and document training in protection of human subjects and the responsible conduct of scientific research.

The computerized data collection and monitoring system consists of a data base system that records clinical and research activities, completion of scheduled assessments, and delivers computerized versions of most of research instruments used in this study. Research assistants use this database to monitor and schedule patients and activities and to administer study assessments. Data entry of non-computerized assessments is accomplished by using specialized data entry software (such as, SPSS Data Entry or Microsoft Access Data base) facilitating efficient data entry and allowing elimination of out-of-range values and double entry of data for detection of key punch errors.

All reports generated from this study will not contain any identifying information about the participants. Research records will be coded only by a number, and will be stored in locked cabinets. Data are stored behind the Yale's firewall on password-protected computers.

Once enrolled, subjects will be given a unique study number, to which only members of our research team will have access. Study data will be kept protected and treated as confidential at all times. Computerized subject data will be password protected. Data will only be reported in aggregate. Data will be de-identified prior to formal data analysis, making individual subject identification impossible. Moveable devices will be encrypted to protect identifiable information, following University policy

Any identifiable information that is obtained in connection with this study will remain confidential and will be disclosed only with subject permission or as required by U.S. or State law. Once enrolled, subjects will be given a unique study number, to which only members of our research team will have access. Study data will be kept protected and treated as confidential at all times. Computerized subject data will be password protected. Data will only be reported in aggregate. Data will be de-identified prior to formal data analysis, making individual subject identification impossible.

Upon completion of the study, all computerized subject datasets will be de-identified and stored in a password-protected study computer, to which only the PI, investigators and study personnel will have access. All paper files with subject information will remain in locked files in the study office of the PI, until they are destroyed, after all analyses are complete.

APPROVED BY THE YALE UNIVERSITY IRB 10/11/2018 VALID THROUGH 10/13/2019  
All clinical aspects of the study, such as treatment delivery and monitoring of subjects' progress or the lack of thereof are also fully documented and supervised. The research team meets weekly to review the overall progress of the study, as well as to review videotaped sessions and/or discuss progress of each subject in the study. All members of the research team, both research assistants and clinicians, are familiar with procedures for identifying and reporting possible adverse reactions.

All adverse events meeting the criteria for expedited reporting are reported to the Yale Institutional Review Board (IRB) using Form 6A for reporting adverse events. The Principal Investigator (PI) reviews all adverse events, classifies the attribution of adverse events (e.g., definitely, probably, possibly related; unlikely or unrelated) and grades the severity of the event, on a 6-point scale (0=no adverse event or within normal limit; 1=mild; 2=moderate; 3=severe; 4=life-threatening; 5=fatal). Serious unanticipated or anticipated adverse events will be reported immediately to NIAAA. The summary will include the number of subjects enrolled and a summary of graded adverse events to date, using the chart format included in the Yale University DSMP template. All serious adverse events will be reported to the local IRB according to local IRB requirements and to the NIAAA project officer within 48 hours. In addition, an annual report will be submitted to the NIAAA Project Officer summarizing all adverse events documented. The PI will evaluate all adverse events and determine whether the event affects the Risk/Benefit ratio of the study and whether modifications to the protocol (e.g., Risks to Subjects) or consent form (e.g., Risks and Inconveniences) are required.

### **Definition of Adverse Event Terms**

**Adverse Event** – Any unfavorable and unintended sign (including an abnormal laboratory finding), symptom, or disease temporally associated with the use of a medical treatment or procedure regardless of whether it is considered related to the medical treatment or procedure (attribution of unrelated, unlikely, possible, probable, or definite). [NIH Guidelines, January 2001]

**Serious Adverse Event (SAE)** – Any adverse drug experience occurring at any dose that results in any of the following outcomes:

1. death,
2. a life-threatening adverse drug experience,
3. in patient hospitalization or prolongation of existing hospitalization,
4. any persistent or significant disability/incapacity,
5. or a congenital anomaly/birth defect.

Important medical events that may not result in death, be life-threatening, or require hospitalization may be considered a serious adverse drug experience when, based upon appropriate medical judgment, they may jeopardize the patient or subject and may require medical or surgical intervention to prevent one of the outcomes listed in this definition. [21CFR312.32(a)]

**Life-threatening Adverse Drug Experience** – Any adverse drug experience that places the patient or subject, in the view of the investigator, at immediate risk of death from the reaction as it occurred, i.e. it does not include a reaction that, had it occurred in a more severe form, might have caused death. [21CFR312.32(a)]

**Unexpected Adverse Drug Experience** – Any adverse drug experience, the specificity or severity of which is not consistent with the current investigator brochure; or, if an investigator

brochure is not required or available, the specificity or severity of which is not consistent with the risk information described in the general investigational plan. “Unexpected” as used in this definition, refers to an adverse drug experience that has not been previously observed (e.g., included in the investigator brochure) rather than from the perspective of such experience not being anticipated from the pharmacological properties of the pharmaceutical product.[21CFR312.32(a)]

### **Attribution**

Assessment of attribution is made by consideration of all clinically relevant data prior to, during, and after occurrence of the event, including diagnostic tests to assess the cause of the event. Clinically relevant data include, but are not limited to; underlying disease, past and present medical history (all concurrent non-malignant disease), concurrent medications, and timing between event and drug administration. The mechanism of action and prior toxicology of the study drug should be considered.

An adverse event is *associated with the use of the drug* when there is a reasonable possibility that the experience may have been caused by the drug. [21CFR312.32(a)]

#### Attribution Standards

- Unrelated:** The Adverse Event is *clearly not related* to the investigational agent(s)
- Unlikely:** The Adverse Event is *doubtfully related* to the investigational agent(s)
- Possible:** The Adverse Event *may be related* to the investigational agent(s)
- Probable:** The Adverse Event is *likely related* to the investigational agent(s)
- Definite:** The Adverse Event is *clearly related* to the investigational agent(s)

## **PRINCIPAL INVESTIGATOR SAE REPORTING REQUIREMENTS**

### **Expedited Reporting of Unexpected SAEs**

*AEs classified as “serious” and “unexpected” that are possibly, probably, or definitely attributed to drug administration, or SAEs whose frequency exceeds expectations, require expeditious handling and reporting.*

The PI will promptly investigate all safety information related to an adverse experience. If the results of the PI’s investigation show an adverse drug experience not initially determined to be reportable (based on whether the event is serious, unexpected, and associated with drug administration) is so reportable, the PI will report such experience. Follow-up information to a safety report shall be submitted as soon as the relevant information is available.

### **Reporting to the Yale Human Investigation Committee**

All SAEs, whether originating at Yale or a collaborating center, meeting the criteria for expedited reporting will be reported to the Yale University Human Investigation Committee (HIC) using HIC Form 6A within 48 hours of discovery.

The Yale University Human Investigation Committee expedited reporting criteria are:

- a. Serious AND unanticipated AND possibly, probably or definitely related events;
- and

b. Anticipated Adverse Events occurring with a greater frequency than expected.

The HIC does not require reporting of any other Adverse Event type. A copy of the HIC Adverse Event Policy is available at:

<http://info.med.yale.edu/hic/policy/AdverseEventPolicy.pdf>

### **Reporting to Alkermes**

Serious Adverse Events, regardless of attribution, shall be reported to Alkermes on FDA Form 3500 within 1 business day of discovery via fax or email:

Alkermes, Inc.

Attention: Alkermes Drug Safety

Dedicated Safety [contact]

Dedicated email: [[contact]](mailto:[contact])

The written report must include the opinion of the study site's PI or designated sub-investigator as to whether the event is related to the study drug. If this relationship is determined to be possibly, probably, or definitely related to study drug, evidence to support this assessment must be provided.

The PI is responsible for monitoring the data and conducting performance and safety reviews, at the specified frequency. Either the PI or the IRB have the authority to stop or modify the study. The monitoring by the IRB will occur annually at the time of re-approval. The PI will conduct data and safety review at least quarterly and at any time a serious adverse event occurs. During the review process, the PI will evaluate whether the study should continue unchanged, requires modification or amendment to continue, or should be closed to enrollment.

During the follow-up period, any patient requiring additional intervention due to significantly increased alcohol consumption or serious psychiatric/medical symptoms will receive a referral to treatment. In addition, any and all adverse events during the follow-up period will be reported to the IRB and the Project Officer at NIAAA with serious adverse events being reported within 48 hours.

We plan to comprise the Data Safety and Monitoring Board (DSMB) with experts in antiretroviral medications and addiction pharmacotherapies. The DSMB will review the progress of the study, and also conduct an interim analysis. The DSMB will monitor the occurrence and frequency of serious adverse events on a quarterly basis and review the results of the interim analysis. The interim analysis will be conducted six months after 40 subjects have been randomized to either of the treatment groups or when all of the 40 subjects in each group have completed the treatment protocol, whichever comes first. The interim analysis will evaluate whether the proportion of subjects achieving >95% adherence differs significantly (at  $p < .05$ ) by treatment condition. This interim analysis will determine whether one of the interventions is significantly inferior to the other on the primary outcome of improving HAART adherence.

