Randomization: Eligible participants will be randomly assigned to VIVITROL + MM/MC or placebo + MM/MC by the investigational pharmacist. All staff, other than this individual and the study biostatistician(s), will be blind to treatment allocation. Subjects will be assigned to one of the two conditions using stratified randomization. There will be 6 strata: (a) participating clinic (3) and (b) alcohol abuse/dependence (Yes/No; 2) in the randomization scheme.

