**Specific Aim 3a:**

To compare differences between the two treatment conditions in the impact on viral mutations, we will use descriptive statistics to report the prevalence of current HIV drug resistance mutation patterns at baseline and at 24-weeks, 9 and 12 months. HIV resistance mutations, as defined by the International AIDS Society guidelines [138], will be evaluated. We will evaluate the association between heavy drinking and HIV viral mutations first in a dichotomous way. We will evaluate the bivariate association of heavy drinking and viral mutations and conduct a chi-square evaluation that contrasts the development of HIV viral mutations (positive vs. negative) with heavy drinking (yes vs. no). Subsequently we will conduct exploratory analyses using multinomial logistic regression to adjust for the potential effects of prior resistance mutations, antiretroviral medication class, duration of HIV disease, and duration of HAART. We will explore the effect of HAART adherence on the relationship between heavy drinking and the development of HIV drug resistance using sequential modeling to test for a potential mediating effect of HAART adherence. Finally, we will conduct an exploratory analysis to determine if the presence and quantity of minor variants affects virologic and HIV outcomes.

To compare differences between the treatment conditions, monthly CD4 lymphocyte counts and HIV RNA will be evaluated using the Mixed Models repeated-measures analysis controlling for baseline differences. To compare differences between the treatment conditions on their impact on liver function tests and Fib-4, we will use the Mixed Models repeated-measures analysis controlling for baseline differences.

We also plan to explore the effect of the treatment conditions on sexual risk behaviors (as measured by the HRBS on a monthly basis). A Mixed Models repeated-measures analysis will be used to evaluate treatment group, time, and interaction effects. We will also collect data on baseline hepatitis status, depressive symptoms at baseline and at the completion of the study, and any side effects reported by patients during the course of the study.

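### No planned analysis compares marked AST/ALT rises between arms: the final liver analysis is on means, and the DSMB's named safety task is serious adverse events

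*Combined protocol and SAP*

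**What the plan says.** **Individual monitoring.** Section V.3 (Assessments) schedules AST, ALT and GGT monthly. Section IX.2 (Minimizing Risks) sets a pathway for "a subject whose AST or ALT rises to > 5 times the upper limit of normal": the test is repeated, and study medication ends if the rise persists or the patient is symptomatic.

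**Oversight during the trial.** Section IX.3, in the paragraphs after the Alkermes reporting instructions, gives the DSMB the progress of the study, serious adverse events ("The DSMB will monitor the occurrence and frequency of serious adverse events on a quarterly basis") and an interim analysis of "whether the proportion of subjects achieving >95% adherence differs significantly". Liver tests and discontinuations are not named, and the text does not say that events are shown by arm. "The Principal Investigator (PI) reviews all adverse events, classifies the attribution of adverse events" and also carries out the safety review at least quarterly. On blinding, Section V.3 (Randomization) says: "All staff, other than this individual and the study biostatistician(s), will be blind to treatment allocation". The one other exception is the investigational pharmacist.

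**Definition of serious.** Under Definition of Adverse Event Terms, an abnormal laboratory finding is an adverse event. Without death, threat to life, hospitalisation or disability, it is serious only if judged an important medical event.

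**Final analysis.** For liver function tests and FIB-4, Section V.4 (Specific Aim 3a) says "we will use the Mixed Models repeated-measures analysis controlling for baseline differences". No count above a limit is planned. Section V.3 lists alcohol-HAART hepatotoxicity as a secondary outcome without an event definition, while Section V.1 places liver function tests under exploratory Aim 3b.

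**The concern.** Liver injury from a drug typically shows as a large rise in a few patients, not as a small shift in everyone. A model of average enzyme values dilutes such rises over all patients and all months. Here it may also offset them: if treatment reduces drinking, enzymes may fall in many treated patients while rising sharply in a few. Section VI.2 itself cites a 15% greater reduction in liver enzymes with naltrexone than with placebo in an earlier study.

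During the trial, a marked rise that is not judged serious lies outside the DSMB's named safety task. It goes to a principal investigator who falls under the general blinding of staff. Alcohol, antiretroviral drugs and hepatitis C (about 30% co-infection, Section V.2) all raise enzymes, so a count pooled over arms cannot show whether the drug adds to them.

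Section V.2 gives reassuring clinicians about tolerability as the goal of the study. On the present plan, it could report reassuring hepatic results without having compared the arms where harm would most likely appear. The large earlier trial cited in Section VI.2 reported both mean enzymes and the proportion of patients above 3 times ULN; this plan keeps only the means.

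**Working it through.** **Sample size.** 154 patients at 1:1 is 154/2 = 77 per arm. The plan's only power figure is for adherence: 72% for 20% against 40% at alpha 0.05. It reproduces: the continuity-corrected two-sided formula gives 77 per arm, and exact enumeration at 77 per arm gives 73.0%. No figure is stated for any hepatic comparison.

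**Assumptions not in the documents.** ULN 40 U/L; within-patient correlation 0.6; baseline plus six monthly ALT values; one monthly value at 6 × ULN = 240 U/L in affected patients. Two ALT spreads were used:
- narrower: median 45, log SD 0.6 (assumed)
- wider: median 36, quartiles 21 and 74, from the naltrexone cohort table in Section IX.1, so log SD = ln(74/21)/1.349 = 0.93

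**Why the mean misses the rises (narrower spread).** Mean ALT is about 45 × exp(0.6²/2) = 53.9 U/L.
- One spike month in six, at 10% against 2%, raises the active mean by about (0.10 − 0.02) × (1/6) × (240 − 53.9) = 2.5 U/L.
- A 15% fall lowers it by 0.15 × 53.9 = 8.1 U/L.
- The net change is about −5.6 U/L, so the mean favours the drug despite the excess of marked rises.
- The excess needed merely to bring the raw means level is 8.1/(186.1/6) = 0.26, or 26 percentage points.

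**Simulated chance of a signal towards harm.** Means were compared by baseline-adjusted ANCOVA, as a stand-in for the mixed model, on raw and log scales. Counts of patients with any value above 5 × ULN were compared by Fisher's exact test. Ranges are over repeated runs.

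| Marked rises, active vs placebo | Fall in treated patients | Means | Count, log SD 0.6 | Count, log SD 0.93 |
|---|---|---|---|---|
| 10% vs 2% | 15% | about 0% | 22–24% | 5–9% |
| 15% vs 2% | 15% | about 0% | 56–62% | 20–26% |
| 10% vs 2% | none | 5–12% | 32–33% | 16% |

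With the wider spread, about 12% of placebo patients exceed 5 × ULN at some visit, which is why the count loses power. For 5% against 2% with the fall, its power there is about 1%.

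**A case favourable to the count.** With the wider spread, spikes to 8 × ULN = 320 U/L in active patients only, no fall, and no other value above 5 × ULN, a 10% rate moves the mean by about 0.10 × (1/6) × (320 − 55.7) = 4.4 U/L, where 55.7 = 36 × exp(0.93²/2) with the unrounded log SD. The means test is then significant in about 8% (log) to 18% (raw) of trials and the count in about 80%. At a 5% rate the figures are 5–9% and 18%.

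**What the table would show.** At 77 per arm, 6 against 0 patients gives Fisher p = 0.028, and 5 against 0 gives p = 0.058. For 8 against 2 patients, the risk difference is 8/77 − 2/77 = 10.4% − 2.6% = 7.8 points. The Wilson limits are 5.4–19.2% and 0.7–9.0%. Newcombe's method combines them into a 95% CI of about −0.3 to 16.8 points. A reader would see that a sizeable excess had not been excluded, which a difference in means would not reveal.

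**The case against.** The strongest reply is that the liver is already watched closely. Tests are monthly, side effects are collected at every treatment visit, and the Section IX.2 pathway acts on marked rises. This stands: a reader might infer that such rises go unmonitored, and the documents do not support that. Only the comparison between arms is missing.

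There are also other reporting routes. A persistent rise that ends treatment could be judged an important medical event and so reach the DSMB. The HIC's expedited criteria include anticipated events occurring more often than expected, and NIAAA receives an annual summary of adverse events. These count, but the first depends on judgment, the second gives no expected rate, and none is stated to be by arm.

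A reader might also infer that nobody who knows allocation has the liver data. The documents do not say so: the biostatistician is unblinded and nothing withholds laboratory results from that role. The investigator's blinding, in turn, follows from the reference to all staff and is not stated by title.

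Nor do the documents make hepatotoxicity the leading drug risk. Sections VI.2 and IX.1 call gastrointestinal effects the most frequent, and Section IX.2 calls the hepatic risk low at this dose. The cited large trial found no effect on the proportion above 3 times ULN. In the Section IX.1 cohort table the upper quartiles rose (AST 80 to 139, ALT 74 to 115), but the cohort is uncontrolled and both p-values are .2. It cannot show drug injury, and no planned analysis rests on it.

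Finally, the simulated sizes rest on assumed rates, and the 15% fall was applied to every treated patient although the source is a group-level figure. That is fair: it limits the size of the claim but not its direction.

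**Conclusion.** The point holds as a gap in the comparison between arms, not in the care of individual patients. The only stated by-arm liver analysis is a mixed model, the DSMB's named safety task reaches non-hospitalised enzyme rises only by judgment, and no count of marked rises by arm is planned during or after the trial.

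Under assumed excesses of 10–15% against 2% with a 15% general fall, a means test signals harm in about 0% of trials and a by-arm count above 5 times ULN in roughly 8–60%. Without the fall, at 10% against 2%, the figures are 5–12% and 16–33%. These depend on the assumed ULN, spike height, within-patient correlation and ALT spread; they illustrate the mechanism and do not forecast the trial's result. At this sample size the count is descriptive, and its value lies in the estimate and its interval. The documents give no evidence that such an excess will occur.

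**What to change.** 1. In Section V.4, beside the mixed model for liver tests, add the number and proportion of patients per arm with any on-treatment AST or ALT above 3 times and above 5 times ULN, each with a risk difference and 95% CI. Label the table descriptive. Both limits already appear in the protocol (Sections VI.2 and IX.2).
2. In the DSMB paragraph of Section IX.3, have the already unblinded biostatistician supply the same by-arm counts, together with liver-related discontinuations, at each quarterly review alongside serious adverse events.

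The thresholds and steps for managing individual patients stay as they are. The laboratory values are already collected monthly, so the cost is one extra table, a few sentences of protocol wording and slightly more unblinded output each quarter.
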